## 6 Methods: Monitoring

### 6.1 Study Steering Committee

Whilst this is deemed to be a low-risk study, a steering committee will be appointed to provide trial oversight and meet once a year to review study progress, adherence to the protocol and safety of study participants. Any study related adverse events will be documented and reported to the Steering Committee. The Steering Committee members are investigators and experts in HIV program, epidemiology and statistics.

### 6.2 Data monitoring

Study progress and safety will be reviewed annually (and more frequently if needed) during the intervention. An annual report will be compiled and will include a list and summary of adverse events. In addition, the annual report will address (1) whether adverse events rates are consistent with pre-study assumptions; (2) reason for dropouts from the study; (3) whether all participants met entry criteria; (4) whether continuation of the study is justified on the basis that additional data are needed to accomplish the stated aims of the study; and (5) conditions whereby the study might be terminated prematurely. The institutional review boards and other applicable recipients will review progress of this study on an annual basis.

### 6.3 Ethical issues arising from the project and measures to address them

The study poses minimal risks to the participants. As with any research study there are possible associated risks.

**Experience of stigma linked to participation** - Distributors and recipients of HIVST kits may experience stigma from fellow community members if they are perceived to be individuals who are part of peer networks adopting high risk sexual behaviour. We will mitigate this in two ways, firstly in our community engagement process by reinforcing the message that all men aged 18 and over are eligible to participate in the study regardless of their behavioural risk profile or HIV status and secondly by ensuring any meetings or phone calls with the distributors remain private and confidential. When the study team contact participants by phone they will confirm their identity and ask if they are in a location where they can speak confidentially. If not, they will arrange a time for a follow-up call when the respondent is in a private setting.

**Psychological harm associated with the HIV self-test result.** There is a risk of psychological harm associated with an individual obtaining a positive/reactive HIV self-test without having support from trained counsellors. To mitigate this the study materials will confirm that the result is not definitive and should be confirmed through a facility test, a free toll helpline will be also implemented and will provide support and counselling through the testing process. There is no evidence of there being an increased risk of harm associated with HIV self-testing when compared to facility based testing. [13]

**Provision of third-party information & identities.** In providing contact information for peer's respondents are providing information on third parties. Such information may include the existence of a relationship hidden from many other people that would not typically be public information. Such information might cause social harm if passed to others in the community. Additionally, individuals outside the study are being included in the study prior to providing consent to be so involved. Revelation of third-party identities is common in research contexts such as this (e.g., when conducting proxy interviews about household members with household heads). Furthermore, it has been argued that the information provided by respondents about contacts is theirs to give, i.e. respondents are providing their view of relationships with others. [59] Specifically, this author argues that the network contacts of respondents are not

human subjects under the United States' Common Federal Rule "as no interaction occurs and name, address, and knowledge of participant-associate contact generally are not likely to be private information", and thus consent is not required. Nevertheless, this does not negate the potential harm that would be caused if study information were made public.

We have evaluated our collection of third-party information under an existing ethical framework on obtaining third-party identities for research proposed [60]. Here the authors suggested that such data collection should be conducted only when three criteria are met:

- i. **No other method is available.** This is the case for any sociocentric analysis, since only by asking respondents to identify their social contacts can connections between responses be made.
- ii. **Third-party identities are maximally protected.** This study will never collect third-party identities outside of an encrypted electronic environment. These identities will be held within datasets using project-specific identifiers, the linkage for which is held by key employees only. At no point will information provided by one participant be provided to another.
- iii. **Benefits outweigh harms.** Stakeholders here include respondents, third parties and the broader public. Respondents' social connections are central to understanding social norms, which in turn are central to understanding HIV-related risk in a community with a generalized HIV epidemic. In this setting, these data therefore have a strong potential to benefit all community members. All proposed study instruments will be developed with the community advisory boards and community-based groups. The study will intentionally not focus primarily on sexual relationships with named contacts, asking only sufficient questions to identify peers and make contact prior to obtaining informed consent.

## 6.4 Harms/Adverse events

Adverse Events that are unanticipated, serious, and possibly related to the study intervention will be reported to the SMC, IRBs and NIH in accordance with requirements.

### 6.4.1 Adverse event definitions

Adverse event (AE): An AE is any unfavourable and unintended harm directly or indirectly incurred by participation in any aspect of the proposed study. This includes symptom and disease incidences due to medical procedures, as well as material, psychological or social harm as an indirect consequence of participation in the study.

Serious adverse event (SAE): SAE is any AE that results in death, life-threatening situation, hospitalisation, or persistent or significant disability or incapacity. All AEs and SAEs are graded according to their seriousness, causality, and expectedness.

*Classification of AEs and SAEs*

Severity: Non-serious AEs are graded according to their severity:

*Mild:* An experience that is transient, and requires no special treatment or intervention. The experience does not generally interfere with usual daily activities.

*Moderate:* An experience that is alleviated with simple therapeutic treatments. The experience may impact usual daily activities.

**Severe:** An experience that requires therapeutic intervention to prevent the AE from becoming a SAE, i.e., to prevent death, a life-threatening condition, hospitalisation, or persistent disability or incapacity.

**Causality:** All AEs and SAEs will be graded according to their causal relationship to the participation in the study.

**Unrelated:** There is no evidence of the adverse event being related to the study procedures (i.e., another cause of the event is most plausible and/or a clinically plausible temporal sequence is inconsistent with the onset of the event).

**Possible:** There is some evidence to suggest a causal relationship between the adverse event and the study procedures as the event follows a reasonable temporal sequence from the initiation of study procedures, but that could readily have been produced by a number of other factors.

**Probable:** There is evidence to suggest a causal relationship between the adverse event and the study procedures and the influence of other factors is unlikely.

**Definitely:** There is clear evidence to suggest a causal relationship between the adverse event and the study procedures and other possible contributing factors can be ruled out.

**Expectedness:** All AEs and SAEs will be graded according to their expectedness:

**Expected:** The adverse event was expected under the risks anticipated for study participants of this study as outlined in the protocol.

**Unexpected:** The adverse event was not expected under the risks anticipated for study participants of this study as outlined in the protocol.

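### Section 6.4.1 makes causation part of the adverse event definition, then grades every event on a causality scale that includes Unrelated and Possible

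*Protocol*

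**What the plan says.** The definition in section 6.4.1 of the protocol is causal: "An AE is any unfavourable and unintended harm directly or indirectly incurred by participation in any aspect of the proposed study". The examples that follow it are causal too: "This includes symptom and disease incidences due to medical procedures, as well as material, psychological or social harm as an indirect consequence of participation". Serious events are defined as a subset: "SAE is any AE that results in death, life-threatening situation, hospitalisation, or persistent or significant disability or incapacity".

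The same section then sets the grading: "All AEs and SAEs will be graded according to their causal relationship to the participation in the study". There are four grades: Unrelated, Possible, Probable and Definitely. The lowest is described in these words: "There is no evidence of the adverse event being related to the study procedures", with the gloss that another cause is most plausible or that the timing does not fit. Possible is for events with some evidence of a link that other factors could easily have caused.

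Three other places use the definition:

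- Section 6.1: "Any study related adverse events will be documented and reported to the Steering Committee".
- Section 6.2: "An annual report will be compiled and will include a list and summary of adverse events". The report also considers whether event rates agree with what was assumed before the study.
- Section 6.4: "Adverse Events that are unanticipated, serious, and possibly related to the study intervention will be reported to the SMC, IRBs and NIH".

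**The concern.** An event definition normally decides what is written down, and the causality grade is a later, documented judgement on what was written down. Here the definition already contains the causal judgement. A team member who hears of a death or hospital admission and applies the definition as worded must first decide whether participation brought it about. If the answer is no, or unclear, the event is not an AE, and the protocol gives no other route by which it is recorded and graded.

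At stake is the completeness of the safety record. The annual review in 6.2 works from AEs, so it can see a pattern only among events that the definition lets in. A pattern in events whose cause looks doubtful one at a time is what such a review should be able to detect. Section 6.3 names stigma and psychological harm after a self-test result as risks, and for harms of that kind attribution is often uncertain when the event first becomes known.

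**Working it through.** No arithmetic applies: the protocol gives no event rate, and the point depends on no sample size or power figure. The check sets the passages side by side.

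**Step 1: the definition.** Let P be the harms brought about, directly or indirectly, by participation. Under 6.4.1 an event is an AE only if it is in P. An SAE is an AE with a serious outcome, so every SAE is also in P.

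**Step 2: the Unrelated grade.** It describes an event with no evidence of a link. Such an event is not in P, so by Step 1 it is not an AE. In strict logic no event can meet the definition and also be correctly graded Unrelated.

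**Step 3: the Possible grade and section 6.4.** An event graded Possible may well have another cause, so whether it is in P is unknown. Yet 6.4 sends on unanticipated serious events that are only possibly related. The test for being an AE is therefore stricter than the test for escalating one. A serious event of uncertain cause could fail the definition and still be the kind of event that 6.4 means to escalate.

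**Step 4: can participation and procedures be separated?** The definition speaks of participation, while the Unrelated grade speaks of study procedures. A harm of participation might then be unrelated to any procedure, and the grade would not be empty. This does not work, because the grading instruction in 6.4.1 is itself set against participation.

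**Step 5: does another section settle it?**

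| Place | What it implies |
|---|---|
| 6.4.1, definition, examples and SAE wording | Narrow: only harms caused by participation |
| 6.4.1, grading instruction and scale | Wide: events of any cause are graded |
| 6.1 | Qualifies events as study related, which would be redundant under the narrow definition and so hints at a wide one; but it commits only to documenting the related part |
| 6.2 | No qualifier of its own; inherits whatever the definition admits |
| 6.4 | Selects by relatedness from a larger pool, so wide |

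No section says that deaths or hospitalisations are recorded whatever their presumed cause.

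**Step 6: a test case.** An enrolled man is admitted to hospital some weeks after receiving a kit, with no known link to the study. By the definition, this is not an AE and nothing need be recorded. By the grading instruction, it is an SAE graded Unrelated. Staff cannot do both.

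**The case against.** The strongest reply is that the definition is one loosely drafted sentence and the rest of the plan shows what was meant. Grading all events for causality, the relatedness qualifier in 6.1 and the selection rule in 6.4 all make sense only if a wider set is recorded first. That stands as evidence of intent. It does not remove the contradiction, because the definition is the sentence that tells staff what to record.

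Several stronger readings are tempting, and the protocol does not support them:

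- *Helpline or field staff screen events informally, and what they reject is never recorded.* No section describes such a step, names anyone to carry it out, or forbids recording.
- *Section 6.1 documents only related events.* It commits to documenting those; it does not exclude others.
- *A suicide attempt after a reactive test, or an assault linked to participation, would be lost.* The definition covers indirect consequences and names psychological and social harm, so these largely fit it. Deaths and admissions whose link is doubtful or presumed absent are more exposed.
- *The Unrelated count must be zero.* An event first suspected to be a consequence of participation can be graded Unrelated on review. The category is empty in logic, not necessarily in the data.

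Two further objections hold. The annual report in 6.2 also considers reasons for dropping out, so some deaths or admissions could surface that way. And recording every AE of any cause would need safety follow-up that the protocol does not schedule for men who do not start PrEP or ART. That limits how far the fix should go.

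**Conclusion.** The contradiction is real and lies within section 6.4.1 itself: the definition and the causality scale cannot both be applied as written, and the definition is also out of step with the escalation rule in 6.4. If staff follow the definition literally, serious events of uncertain or presumed unrelated cause could be left out of the causality grading and the annual summary.

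The size is modest and cannot be stated as a number, since the protocol gives no event rate and the number of men enrolled is not a count of missed events. The protocol rates the study as low risk, onward reporting is in any case limited to serious events that are possibly related, and the primary and secondary outcomes are unaffected. The conclusion assumes that the definition governs what is recorded, and that no separate safety procedure, which this protocol does not mention, already captures all deaths and hospitalisations. It does not assume that any event has been or will be omitted.

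**What to change.** In section 6.4.1, remove the causal condition from the definition, at least for SAEs and social harms. Suitable wording would be: any serious event or social harm in an enrolled participant that becomes known to the study team is recorded, whether or not it is considered related, and causality is graded afterwards. The four-grade scale can then be used as it stands.

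In section 6.1, replace the relatedness qualifier so that the sentence covers the same recorded set. Leave the onward-reporting rule in section 6.4 unchanged; it would then select from a recorded and graded pool.

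Limiting the rule to events that become known avoids any new scheduled contact. The cost is the rewording and a few additional event forms. Extending it to all non-serious events of any cause is not proposed, because that would need follow-up the protocol does not plan.

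### Section 6.4.1 counts social and material harm as adverse events, but lasting social harm fits none of its severity grades and no seriousness criterion addresses it

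*Protocol*

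**What the plan says.** Protocol section 6.4.1 defines an AE to include symptoms and disease, "as well as material, psychological or social harm as an indirect consequence of participation in the study". The seriousness rule follows: "SAE is any AE that results in death, life-threatening situation, hospitalisation, or persistent or significant disability or incapacity".

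The same section says that "Non-serious AEs are graded according to their severity" and gives three grades:

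- **Mild:** "An experience that is transient, and requires no special treatment or intervention"; in addition, "The experience does not generally interfere with usual daily activities".
- **Moderate:** "An experience that is alleviated with simple therapeutic treatments", with a possible effect on daily activities.
- **Severe:** therapy is needed to stop the event from reaching one of the SAE outcomes.

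Section 6.3 names three risks: stigma, psychological harm after a self-test result, and harm from third-party information. On the first it says that "Distributors and recipients of HIVST kits may experience stigma from fellow community members". On the third it says "Such information might cause social harm if passed to others in the community".

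Reporting is set out in three places. Section 6.1 sends study-related AEs to the Steering Committee. Section 6.2 puts a list and summary of AEs in the annual report. Section 6.4 sends an event to the SMC, the IRBs and NIH only if it is unanticipated, serious and possibly related, all three together.

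**The concern.** The AE definition is wider than the scales applied to it. A social harm is admitted as an AE, but the rules that then decide how grave it is were written for medical events. In a trial of peer-distributed self-test kits, social harm is a main foreseeable risk. Section 3.3.1 has peers' names and phone numbers collected before those peers consent, and pays the initial distributor for each person who attends the clinic for a confirmatory test.

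The harms record is what is at stake. If a grave social harm cannot be graded and is non-serious by default, the annual summary cannot separate it from a trivial one. An unforeseen event of this kind would also not qualify for reporting under section 6.4.

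**Working it through.** The protocol gives no figure on this point, so the check is logical: apply the 6.4.1 definitions as written to harms of the kind that 6.3 anticipates.

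**Seriousness.** The four criteria are death, a threat to life, hospitalisation, and disability or incapacity. Criteria that are a social or material outcome: 0 of 4. A social harm becomes serious only through one of these consequences.

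**Severity.** The four cases below are constructed for this check.

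| Case | Mild? | Moderate? | Severe? | Grade |
|---|---|---|---|---|
| 1. Brief stigma, daily life undisturbed | Yes: transient, needs nothing, no interference | Not needed | No | Mild |
| 2. Distress relieved by simple therapy | No: needs treatment | Yes | No | Moderate |
| 3. Lasting loss of home or livelihood after disclosure | No: not transient, and it interferes with daily life | No: simple therapy does not relieve it | No: no therapy is needed to avert an SAE outcome | None |
| 4. Brief social harm that disrupts daily life, with no therapy for it | No: it interferes with daily life | No: simple therapy does not relieve it | No: as in case 3 | No clear grade |

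Cases 1 and 2 show that the scale works for some non-medical harm. Cases 3 and 4 show where it fails: social harm that is persistent or disruptive and has no therapeutic remedy. Section 6.4.1 nevertheless says that non-serious AEs are graded, and cases 3 and 4 are non-serious unless a listed outcome follows.

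**Reporting.** Follow case 3 through each route:

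- Section 6.1: if study-related, it reaches the Steering Committee, which meets once a year. Seriousness is not required.
- Section 6.2: it appears in the annual AE list, which is not limited to serious events, but without a grade.
- Section 6.4, if the harm is of a kind named in 6.3: it fails on being unanticipated as well as on seriousness. A new seriousness criterion alone would leave this unchanged.
- Section 6.4, if the harm is not named in 6.3 (for example violence without a medical consequence, or coerced testing): it could count as unanticipated and possibly related, and would then fail on seriousness alone. Here the definition decides the outcome.
- Section 6.4.2: a protocol violation is reported in the same way as an SAE. This could cover a confidentiality breach by the study team, but not harm done by peers or community members.

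**The case against.** The strongest reply is that pairing a broad AE definition with medical seriousness criteria is not a contradiction, that oversight already sees these events, and that no trial result depends on it. Much of this stands. Sections 6.1 and 6.2 do not filter on seriousness, and the primary outcome and its analysis are unaffected. It does not answer the grading gap: the protocol says that non-serious AEs are graded, and its scale cannot grade case 3.

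A reader might infer more than the protocol supports, in five ways:

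- *That severity is defined purely in medical terms.* It is not. Mild uses transience, and both mild and moderate refer to daily activities.
- *That the count of serious social harms is fixed at zero.* It is not. Any AE that leads to a listed outcome is serious. The wording on threats to life could cover an assault, and disability or incapacity is not limited to physical harm.
- *That a new seriousness criterion would send stigma and disclosure harm to the IRBs and NIH.* It would not, because these are anticipated in 6.3 and section 6.4 also requires the event to be unanticipated.
- *That continuation of the trial is judged from the AE list.* Section 6.2 ties that item to whether more data are needed to meet the study's aims.
- *That ungradable harms will be frequent, or that a rate limit can be put on them.* The protocol gives no frequency for social harm and plans no statement that serious harm was absent.

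**Conclusion.** The point holds in a limited form. Section 6.4.1 admits social and material harm as AEs but has no seriousness criterion for them (0 of 4). Its moderate and severe grades rest on therapy, so persistent or disruptive social harm without a therapeutic remedy has no grade. Two of the three risks in 6.3, stigma and third-party disclosure, are social, so the gap touches harms of the kind the trial expects. How many events it would affect cannot be derived from the protocol.

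The consequences are an annual AE summary in which some grave events carry no grade, and no route under 6.4 for a grave social harm that 6.3 did not foresee and that has no listed medical consequence. The conclusion assumes that the definitions are applied as written, without an unwritten convention for social harms. It is a gap in a stated safety rule that should be closed. It does not threaten the efficacy analysis.

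**What to change.** 1. In 6.4.1, for non-medical harm, anchor mild, moderate and severe to duration and interference with daily life instead of to treatment.
2. In 6.4.1, add a seriousness criterion for grave material or social harm. Candidates to consider are violence or a credible threat of it, disclosure of a test result or HIV status without consent, coerced testing, and loss of home, livelihood or family support.
3. In 6.4, state how serious social harms already anticipated in 6.3 are reported, because the requirement that an event be unanticipated would otherwise still exclude them.
4. In 6.2, show social harms as their own line in the annual AE summary.

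The cost is about one paragraph for the definitions, short additions to 6.2 and 6.4, and extra options on the AE form. The downside is that a few more events will be classed as serious and reported.
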